5.3 Dose Adjustments

5.3.1 Lirilumab and 5-azacytidine dose adjustments for drug-related hematological AEs:

Dose reduction/interruption/discontinuation decisions should be based on the CTCAE version 4.0 (Appendix C) of the toxicity and the guidelines provided below.

- Patients with acute leukemia's usually present with abnormal peripheral blood counts at the time therapy is started and myelosuppression is an expected event during the course of therapy for acute leukemias. Thus, no dose adjustments or treatment interruptions for myelosuppression will be planned for the first 4 cycles and/or in the presence of residual leukemia. After that, treatment interruptions and dose adjustments may be considered according to the following guidelines only when there is no evidence of active leukemia (e.g., only if <5% blasts in the bone marrow or cytopenias not considered to be related to leukemia).
 1. Patients with a response (e.g., only if <5% blasts in the bone marrow or cytopenias not considered to be related to leukemia) and pre-cycle counts of neutrophils $>1 \times 10^9/L$ and platelets $>50 \times 10^9/L$ who have sustained low counts of neutrophils $<0.5 \times 10^9/L$ or a platelet count $<20 \times 10^9/L$ for more than 2 consecutive weeks in the current cycle, may have the treatment with 5-azacytidine interrupted at the discretion of the treating physician after discussing with the PI until neutrophils recover to $\geq 1 \times 10^9/L$ and platelets to $\geq 50 \times 10^9/L$. Lirilumab has not been associated with neutropenia and/or thrombocytopenia in prior studies and should generally not be interrupted for myelosuppression.
 2. If there are persistent peripheral blood blasts, or the bone marrow shows >5% blasts or evidence of leukemia, treatment may be continued regardless of neutrophil and platelet count with supportive care as needed. Dose-interruptions of 5-azacytidine in these patients should be considered on an individual case and discussed with the PI.
 3. Patients with a response (no marrow evidence of leukemia) and pre-cycle counts of neutrophils $<1 \times 10^9/L$ and platelets $<50 \times 10^9/L$ may be continued regardless of neutrophil and platelet count with supportive care as needed. Dose-interruptions in these patients should be considered on an individual case and discussed with the PI.
 4. Investigators should, whenever possible, determine which medication is causing the toxicity and interrupt or dose reduce 5-azacytidine and/or interrupt lirilumab, as applicable. No dose reductions are permitted for lirilumab. Lirilumab has not been associated with neutropenia and/or thrombocytopenia in prior studies and should generally not be interrupted or discontinued for myelosuppression.

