The second (IPH2102-201) is a double-blind, placebo-controlled, Phase 2 trial of lirilumab in patients with AML who are in complete remission but ineligible for allogeneic transplant. One-third of subjects in this study will be receiving placebo. The doses of lirilumab evaluated in this maintenance AML trial were 0.1 mg/kg every 12 weeks and 1.0 mg/kg every 4 weeks. A total of 100 patients have been treated with lirilumab on this trial as of the data cut-off date (July 29, 2014). One hundred one (67%) subjects have treatment ongoing and 50 (33%) subjects discontinued prematurely. In these 50 subjects, the main (or only) reason for study discontinuation was relapse of disease (43 subjects), AEs of pancytopenia (1 subject) and acute febrile neutrophilic dermatosis (1 subject), withdrawal of consent (2 subjects), investigator decision (2 subjects), and suspicion of disease progression (2 subjects). An independent Data and Safety Monitoring Board completed safety analysis of 86 randomized subjects enrolled in this trial. On 11-Mar-2014, the members of this committee recommended continuation of the study without any modification. Adverse events were reported by 121 of 150 (81%) subjects exposed to either lirilumab or placebo. Most of these AEs were mild (Grade 1) or moderate (Grade 2). Thirty-three (22%) subjects reported Grade 3 or Grade 4 AEs (irrespective of causality) including thrombocytopenia in 5 (3%), arthralgia in 1 (<1%), neutropenia in 7 (5%), fatigue in 1 (<1%), weight increase in 2 (1%), and urinary tract infection in 1 (1%) patients. One subject reported Grade 5 pulmonary embolism, and 1 subject reported Grade 5 general physical health deterioration (corresponding to disease progression). Both of the Grade 5 events were considered by the investigator to be unrelated to study drug. Sixty-six of 150 (44%) subjects had AEs considered to be related to the study drug (either lirilumab or placebo). Most related AEs were mild or moderate in severity. Nine (6%) subjects had related Grade 3 AEs (neutropenia in 3 subjects and acute febrile neutrophilic dermatosis, sciatica, myalgia, thrombocytopenia, increased amylase, and bronchospasm in 1 subject each). One subject (0.7%) had a related Grade 4 AE of neutropenia that occurred on Cycle 1/Day 8. Adverse events evaluated as related to study drug and reported in $\geq 3\%$ of subjects were asthenia in 15 (10%) subjects, pruritus in 13 (9%) subjects, chills in 7 (5%) subjects, pyrexia in 6 (4%) subjects, and neutropenia in 5 (3%) of subjects. Five (3%) subjects reported AEs that led to study discontinuation: 4 subjects reported single events that were unrelated to study drug (lirilumab or placebo), and 1 subject reported Grade 3 acute febrile neutrophilic dermatosis that was considered related to study drug. Seventeen (11%) subjects reported SAEs during the study. The only Grade 3 or Grade 4 SAE's (irrespective of causality) seen in more than 1 subject was urinary tract infection in 2 (1%). Only 4 of 20 SAEs were considered to be related to study drug by the investigator, including one case each of Grade 4 neutropenia,

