If prolonged myelosuppression (more than 8 weeks) WITH evidence of a hypocellular marrow (marrow cellularity less than 5% without evidence of leukemia) is observed, 5-azacytidine and lirilumab will be discontinued. Delays in start of subsequent cycles greater than 8 weeks will be acceptable only for patients who are deriving clinical benefit and after discussion with the principal investigator of potential risk/benefit ratio. If the peripheral counts do not recover (ANC $<1 \times 10^9/L$ and/or platelets $<30 \times 10^9/L$) but there is evidence of residual leukemia in the bone marrow, subsequent cycles can be administered at the discretion of the treating physician not earlier than 21 days after the prior cycle.

5.2.2.4 For patients who discontinue therapy, the reason for treatment discontinuation will be captured.

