5.3.4 Lirilumab Discontinuation Criteria

Treatment should be permanently discontinued for the following:

- Any Grade 2 drug-related uveitis or eye pain or blurred vision that does not respond to topical therapy and does not improve to Grade 1 severity within the re-treatment period OR lasting > 7 days with systemic treatment
- Any Grade 3 non-skin, drug-related adverse event lasting > 7 days, with the following exceptions for drug-related laboratory abnormalities, uveitis,

pneumonitis, bronchospasm, diarrhea, colitis, neurologic adverse event, hypersensitivity reactions, and infusion reactions:

- Grade 3 drug-related uveitis, pneumonitis, bronchospasm, diarrhea, colitis, neurologic adverse event, hypersensitivity reaction, or infusion reaction of any duration requires discontinuation
- Grade 3 drug-related laboratory abnormalities do not require treatment discontinuation except those noted below:
- Any drug-related liver function test (LFT) abnormality that meets the following criteria require discontinuation: AST or ALT > 8 x ULN
- Any Grade 4 drug-related adverse event or laboratory abnormality, except for the following events which do not require discontinuation:
 - Isolated Grade 4 amylase or lipase abnormalities that are not associated with symptoms or clinical manifestations of pancreatitis and decrease to < Grade 4 within 1 week of onset.
 - Isolated Grade 4 electrolyte imbalances/abnormalities that are not associated with clinical sequelae and are corrected with supplementation/appropriate management within 72 hours of their onset
- Any dosing interruption lasting > 8 weeks with the following exceptions:
 - Dosing interruptions to allow for prolonged steroid tapers to manage drug-related adverse events are allowed. Prior to re-initiating treatment in a subject with a dosing interruption lasting > 8 weeks the Investigator must be consulted. Tumor/Leukemia assessments should continue as per protocol even if dosing is interrupted.
 - Dosing interruptions > 8 weeks that occur for non-drug-related reasons may be allowed if approved by the Investigator. Prior to re-initiating treatment in a subject with a dosing interruption lasting > 8 weeks the Investigator must be consulted. Tumor/Leukemia assessments should continue as per protocol even if dosing is interrupted.

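### Section 5.3.1 bases its lirilumab rule for myelosuppression on a safety statement that Section 2.4 does not support, and 5.3.1, 5.3.3 and 5.3.4 give different instructions for a drug-related cytopenia without saying which governs

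*Combined protocol and SAP*

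**What the plan says.** Section 5.3.1 covers dose adjustment for drug-related hematological events. Item 1 says: "Lirilumab has not been associated with neutropenia and/or thrombocytopenia in prior studies and should generally not be interrupted for myelosuppression". Item 4 repeats the premise and widens the instruction, so that lirilumab "should generally not be interrupted or discontinued for myelosuppression". The same section plans no adjustment or interruption for myelosuppression in the first 4 cycles or while leukemia persists.

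Section 2.4 summarizes the double-blind maintenance trial in AML (IPH2102-201). It reports: "Nine (6%) subjects had related Grade 3 AEs (neutropenia in 3 subjects and acute febrile neutrophilic dermatosis, sciatica, myalgia, thrombocytopenia", followed by two further single events. It continues: "One subject (0.7%) had a related Grade 4 AE of neutropenia that occurred on Cycle 1/Day 8", and later lists that Grade 4 neutropenia among the related serious events. Among related events of any grade it gives "neutropenia in 5 (3%) of subjects". It also makes clear what related means there: "Sixty-six of 150 (44%) subjects had AEs considered to be related to the study drug (either lirilumab or placebo".

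Three other rules can reach a cytopenia:

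- Section 5.3.3 delays lirilumab for a drug-related Grade 3 laboratory abnormality. The only blood-count exemptions are Grade 3 lymphopenia and leukopenia.
- Section 5.3.4 requires permanent discontinuation for "Any Grade 4 drug-related adverse event or laboratory abnormality, except for the following events which do not require discontinuation". The exceptions that follow are certain isolated amylase or lipase abnormalities and certain isolated electrolyte abnormalities.
- Section 5.2.2.4 (the first of two items with that number) says "5-azacytidine and lirilumab will be discontinued" when myelosuppression lasts more than 8 weeks with a hypocellular marrow and no evidence of leukemia.

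**The concern.** There are two separate problems. First, a dosing instruction is justified by a factual statement that the background section of the same document does not support. A treating physician who reads only Section 5.3.1 is told that earlier trials showed no link between lirilumab and these cytopenias. That physician is then asked, in item 4, to decide which drug is responsible.

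Second, once a neutropenia or thrombocytopenia has been judged drug-related, the outcome for lirilumab depends on which section the physician opens. Two physicians following the protocol faithfully could treat the same patient differently, and a monitor could not say which of them had deviated. What is at stake is consistent patient management and a clear standard for protocol compliance. Nothing here has been shown to change the response analysis or the monitoring boundaries.

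**Working it through.** **Step 1. Reproduce the Section 2.4 figures.** The denominator is the 150 subjects exposed to lirilumab or placebo in IPH2102-201.

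- Related neutropenia, any grade: 5/150 = 3.3% (stated as 3%).
- Subjects with related Grade 3 events: 9/150 = 6.0% (stated as 6%). The listed events add up: 3 neutropenia + 6 single events = 9. One of the six is thrombocytopenia.
- Related Grade 4 neutropenia: 1/150 = 0.7% (as stated).
- Related Grade 3 or 4 neutropenia: 3 + 1 = 4 reports, at most 4/150 = 2.7%. These presumably lie within the 5 any-grade cases and must not be added to them.

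Two other entries in Section 2.4 are left out. The Grade 3/4 counts irrespective of causality do not speak to association. The one withdrawal for pancytopenia is no support either, because the only event leading to discontinuation that was judged related was the neutrophilic dermatosis.

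**Step 2. What the blinded counts allow.** Section 2.4 gives 100 subjects treated with lirilumab, which leaves 150 − 100 = 50 on placebo. If lirilumab had no effect, the expected number of the 5 neutropenia cases in the lirilumab arm would be 5 × 100/150 = 3.3. The pooled count is therefore compatible with no effect and also with an effect. It supports neither a causal claim nor the statement that no association has been seen.

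**Step 3. Set the rules side by side** for a neutropenia or thrombocytopenia judged drug-related:

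| Section | Trigger | Consequence for lirilumab | Cytopenias exempted |
|---|---|---|---|
| 5.3.1 | Drug-related hematological event | Generally continue; item 4 permits interruption where lirilumab is judged responsible | Not applicable |
| 5.3.3 | Drug-related Grade 3 laboratory abnormality | Delay | Lymphopenia, leukopenia |
| 5.3.4 | Drug-related Grade 4 event or laboratory abnormality | Permanent discontinuation | None |
| 5.2.2.4 | Over 8 weeks, hypocellular marrow, no leukemia | Discontinue both drugs | Not applicable |

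**Step 4. Apply the rules to cases.**

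- *Grade 3 neutropenia judged related to lirilumab.* Section 5.3.3 calls for a delay. Section 5.3.1 makes continuing the default and leaves interruption to judgment. Section 5.3.4 does not require permanent discontinuation for Grade 3 laboratory abnormalities outside those it lists, so the divergence at this grade concerns delay only.
- *Grade 4 neutropenia judged related to lirilumab.* Section 5.3.4 requires permanent discontinuation. Section 5.3.1 item 4 says generally not. If the event falls in the first 4 cycles, 5.3.1 also plans no interruption. The Grade 4 case in Section 2.4 arose on Day 8 of Cycle 1.
- *Cytopenia judged related to 5-azacytidine only.* If drug-related in 5.3.3 and 5.3.4 means related to lirilumab, neither section applies. If it means related to either study drug, both do. The term is not defined there.
- *Prolonged myelosuppression with hypocellular marrow.* Section 5.2.2.4 is narrow and specific. It can stand as an exception to the general default in 5.3.1.

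**The case against.** The strongest reply is that Section 5.3.1 is not a prohibition. It says *generally*, and item 4 asks the investigator to identify the responsible drug and allows lirilumab to be interrupted where applicable. A reader might infer that physicians are forbidden to interrupt lirilumab, but the text does not say that. This point stands, and it also disposes of any contradiction with 5.2.2.4.

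Next, 5.3.1 is the section written for hematological events, 5.3.3 is headed for immuno-oncology events, and 5.3.4 is headed for lirilumab. Other text expects cytopenia to come from 5-azacytidine: 5.3.7.4 says so directly, and 5.3.3 lets a patient with pancytopenia stop 5-azacytidine and stay on lirilumab. This narrows the conflict to cytopenias attributed to lirilumab, but does not remove it. Section 5.3.3 names lymphopenia and leukopenia, so blood counts are within its reach. The exceptions in 5.3.4 are a closed list. Item 4 of 5.3.1 itself foresees that lirilumab may be responsible.

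A reader might also infer that lirilumab has been shown to cause cytopenia, perhaps because the chance that all 5 related neutropenia cases fell on placebo is only (1/3)^5, about 0.4%. That figure assumes lirilumab has no effect. It says only that some cases probably fell in the larger arm, which is not evidence of an association. The detailed safety data are in the Investigator Brochure (Appendix E), which was not available for this review.

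Finally, a reader might infer that the premise distorts safety reporting. The documents do not support this. Section 10.4 requires serious events to be reported to the IND Office regardless of attribution, and Section 10.5 requires them to go to the manufacturer whether or not they are related.

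**Conclusion.** The point holds in two limited parts.

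1. The statement in 5.3.1, made twice, is wrong as written against Section 2.4. Related neutropenia was reported in 5 of 150 subjects under blinding (Grade 3 in 3, Grade 4 in 1), and related Grade 3 thrombocytopenia in 1. This conclusion rests only on the reported investigator assessments. It does not assume that any case was caused by lirilumab, and these data could not establish that.

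2. For a neutropenia or thrombocytopenia judged drug-related, 5.3.1 diverges from 5.3.3 at Grade 3 and from 5.3.4 at Grade 4, with no stated precedence and no definition of which drug is meant. The divergence at Grade 4 is the sharper one, because 5.3.4 is mandatory. If drug-related means related to lirilumab, the conflict is confined to cytopenias attributed to lirilumab. If it means related to either drug, it extends to those attributed to 5-azacytidine.

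Section 5.2.2.4 needs only a cross-reference.

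**What to change.** - Reword the statement in 5.3.1 items 1 and 4 so that it agrees with Section 2.4, including the fact that relatedness there was assessed under blinding.
- Reconcile 5.3.1 with 5.3.3 and 5.3.4. State which section governs drug-related neutropenia and thrombocytopenia at each grade, including in the first 4 cycles.
- Say in 5.3.3 and 5.3.4 whether drug-related means related to lirilumab, to 5-azacytidine, or to either.
- Add a cross-reference from 5.3.1 to the prolonged-myelosuppression rule in 5.2.2.4.

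The clinical rule itself is for the sponsor to choose, and no view is offered on it here. The cost is amendment wording: two corrected sentences, a precedence statement, a definition and a cross-reference. The sample size, monitoring boundaries and analysis do not need to change.

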5.3.2 Lirilumab and 5-azacytidine dose adjustments for non-hematologic drug-related AEs

Investigators should, whenever possible, determine which medication is causing the toxicity and interrupt or dose reduce 5-azacytidine and/or interrupt lirilumab, as applicable. No dose reductions (only interruptions) are permitted for lirilumab. Dose reductions of azacytidine will be as per Table 1. Thus, if dose level 0 is established as the MTD, one and two dose level reductions of azacytidine will be azacytidine 50 mg/m² x 7 days and azacytidine 25 mg/m² x 7 days, respectively. If the MTD is below dose level 0 further dose reduction levels of 5-azacytidine will be defined before moving to the phase II portion of the study.

Table 2 Dose adjustments for non-hematologic drug-related adverse events, clinically significant in the opinion of the investigator

Grade	Occurrence	Dose modification
1 or 2	Any time	No dose reduction.
3 or 4 (Persistent grade 2: Consider similar dose adjustments if persistent and not responding to optimal management in the opinion of PI and treating physician)	1st and 2nd time	Hold lirilumab and 5-azacytidine. Resume lirilumab and 5-azacytidine at prior dose if recovery to ≤ Grade 1 occurs within 14 days. If toxicity persists for 15-28 days, hold therapy and resume at ONE dose level below current dose for 5-azacytidine and prior dose of lirilumab ONLY after recovery to ≤ Grade 2. Dose re-escalation to prior dose of 5-azacytidine is permitted in accordance with the dose-escalation guidelines in section 5.3.6.
	3 rd and 4th time	Hold lirilumab and 5-azacytidine. Follow until toxicity ≤ Grade 2. Resume lirilumab at prior dose and 5-azacytidine at ONE dose level below current dose. Dose re-escalation of 5-azacytidine to prior dose is permitted in accordance with the dose-escalation guidelines in section 5.3.6.
	5th time	Hold lirilumab and 5-azacytidine. Follow until toxicity ≤ Grade 2. Resume lirilumab at prior dose and 5-azacytidine at TWO dose levels below current dose. Dose re-escalation of 5-azacytidine by ONE dose level every 4 weeks is permitted in accordance with the dose-escalation guidelines in section 5.3.6.

5.3.3 Lirilumab dose delay/interruption for immune-oncology drug-related AEs, clinically significant in the opinion of the investigator

Lirilumab administration should be delayed for the following drug-related AEs, clinically significant in the opinion of the investigator:

- Any Grade ≥2 non -skin AE, except that
 - Grade 2 fatigue or laboratory abnormalities do not require delay, however
 - ◆ For a subject with baseline AST, ALT, or total bilirubin within normal limits, delay dosing for drug-related Grade ≥2 values
- Any Grade 3 skin AE, or Grade 3 laboratory abnormality, with the following exceptions:

- Grade 3 lymphopenia or leukopenia does not require dose delay.
- If a subject has Grade 1 baseline AST, ALT, or total bilirubin, delay dosing for drug-related Grade 3 toxicity
 - Any AE, laboratory abnormality, or intercurrent illness, which in the judgment of the investigator, warrants delaying the dose of study medication.
 - Lirilumab dose reductions are not permitted in this study (only dose delays when indicated).

Subjects may resume treatment with study drug when the drug-related AE(s) resolve to Grade ≤ 1 or baseline value, with the following exceptions:

- Subjects may resume treatment in the presence of Grade 2 fatigue
- Subjects who have not experienced a Grade 3 drug-related skin AE may resume treatment in the presence of Grade 2 skin toxicity
- Subjects with baseline Grade 1 AST/ALT or total bilirubin who require dose delays for reasons other than a 2-grade shift in AST/ALT or total bilirubin may resume treatment in the presence of Grade 2 AST/ALT OR total bilirubin
- Subjects with combined Grade 2 AST/ALT AND total bilirubin values meeting discontinuation parameters (Discontinuation Section below) should have treatment permanently discontinued
- Drug-related pulmonary toxicity, diarrhea, or colitis, must have resolved to baseline before treatment is resumed
- Drug-related endocrinopathies adequately controlled with only physiologic hormone replacement may resume treatment

If the criteria to resume treatment are met, the subject should restart treatment at the same dose at the next scheduled timepoint per protocol. The next scheduled time point for 5-azacytidine is the projected day 1 of the next cycle. The next scheduled time point for Lirilumab is the projected day 8 of the next cycle. These will be the next scheduled time points irrespective of the patients current dose level. However, if the treatment is delayed past the next scheduled timepoint per protocol, the next scheduled timepoint will be delayed until dosing resumes. Patients who receive combination therapy in whom continuation of 5-azacytidine is considered to be inadequate, or inappropriate (e.g., because of pancytopenia) can discontinue 5-azacytidine and continue with lirilumab only.

If treatment is delayed > 8 weeks, the subject must be permanently discontinued from study therapy, except as specified in discontinuation section.

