5.2.1.1 The starting dose will be dose level -1.

Table 1. Dose levels of 5-azacytidine and lirilumab during the lead-in phase (part a)

Dose level	5-azacytidine (mg/m ² /d, Days 1-7)	Lirilumab (mg/kg, day 8)
-4	25	0.3
-3	50	0.3
-2	75	0.3
-1	75	1.0 (Starting dose)
0	75	3.0

5.2.1.2 The goal of the lead-in phase is to identify the dose at which <2/6 patients experience DLT. During the lead-in phase the dose’s of 5-azacytidine and lirilumab may be reduced if 2 or more patients experience DLT at any given dose. After the lead in phase the dose of lirilumab may not be reduced in the phase II portion of the study. For potential lirilumab related AEs in the phase II portion of the study only dose interruptions of lirilumab will be permitted. Dose reductions or escalations of 5-azacytidine will continue to be permitted in the phase II portion of the study and dose reductions or escalations of 5-azacytidine beyond those mentioned in table 5 or different to the doses specified should be discussed with the PI and documentation of the justification recorded in the chart.

5.2.1.3 The dose and /or schedule of administration is subject to modification pending information from ongoing clinical trials of lirilumab as a single agent and in combination with other drugs.

DLT is defined as clinically significant non-hematologic adverse event or abnormal laboratory value assessed as unrelated to disease progression, intercurrent illness, or concomitant medications and occurring during the first cycle on study that meets any of the following criteria:

- CTCAE Grade 3 AST (SGOT) or ALT (SGPT) for ≥ 7 days
- CTCAE Grade 4 AST (SGOT) or ALT (SGPT) of any duration
- All other clinically significant non-hematological adverse event that is Grade 3 or 4 according to the NCI common terminology criteria version 4.0 with the following exceptions:
 - Grade 3 or 4 nausea, vomiting and diarrhea will be considered DLT only if not controlled by optimal therapy.
 - Grade 3 biochemical abnormalities (e.g., lipase or bilirubin elevation) will only be considered DLT if accompanied by clinical consequences. Grade 3 or 4 electrolyte abnormalities will only be considered DLT if possibly related to study drug and not corrected by optimal replacement therapy.

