5.2.1.4 We will first treat 6 patients at dose level -1 in the lead-in phase. If DLT occurs in $\geq 2/6$ patients, this dose level would exceed the MTD, and 6 patients will be treated at the next lower dose level (i.e. dose level -2). If DLT is observed in the first 28 days of treatment in 0 or 1/6 at dose level -1, then dose level 0 will be evaluated. The dose adjustment (Table 1) will continue in cohorts of 6 until we reach a dose level at which $< 2/6$ patients experience a DLT in the first 28 days. The dose level at which 0-1/6 patients experience a DLT in the first 28 days of treatment will be the MTD and will be used to treat an additional 34 patients in the phase II portion of the study. If $\geq 2/6$ patients experience DLT at dose level -4, the study will be revised to consider additional lower dose levels (based on potential synergistic toxicity).

5.2.1.5 Patients that are removed from study before day 28 for any reason other than toxicity and have not experienced DLT will be replaced.

5.2.2 One cycle of therapy is defined as 28 days. Patients will receive one cycle of therapy every 28 days (+/- 7 days).

5.2.2.1 In the phase II part of the study (once the MTD dose has been defined) cycles may be started early (but not earlier than day 21) for patients with active disease if judged in the best interest of the patient.

For the lead-in cohort, DLT defining period is 28 days. As such, cycle 2 should not be started before 28 days for the patients being treated on the lead-in cohort.

5.2.2.2 Subsequent cycles may be delayed for recovery of toxicity or other medical conditions (e.g. infections). Delays in start of subsequent cycles greater than 8 weeks will be acceptable only for patients who are deriving clinical benefit and after discussion with the principal investigator of potential risk/benefit ratio.

5.2.2.3 In instances where one drug has to be discontinued transiently because of safety, the administration of the other drug may continue as scheduled. If the drug that is held can resume at a later time, no doses will be made up and the administration will follow the originally defined schedule calendar according to the drug that was continued.

5.2.2.4 Subsequent courses of 5-azacytidine and lirilumab may be administered regardless of peripheral blood counts during the first 4 cycles and/or in the presence of residual leukemia.

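### Table 2 tells staff to resume lirilumab after severe drug-related events for which section 5.3.4 requires permanent discontinuation, and nothing says which rule governs

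*Combined protocol and SAP*

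**What the plan says.** **Lirilumab restart, section 5.3.2 and Table 2.** Section 5.3.2 asks the investigator to identify the causative drug where possible and bars any lirilumab dose reduction. For Grade 3 or 4 non-hematologic drug-related events, Table 2 then holds both drugs and sets the restart:

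- First and second occurrence: both drugs restart at the prior dose if the event falls to Grade 1 or lower within 14 days. If it lasts 15 to 28 days, therapy is held and staff are to "resume at ONE dose level below current dose for 5-azacytidine and prior dose of lirilumab ONLY after recovery to ≤ Grade 2".
- Third and fourth occurrence: the patient is followed to Grade 2 or lower, lirilumab resumes at the prior dose, and 5-azacytidine resumes one level down.
- Fifth occurrence: the same, with 5-azacytidine two levels down.

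No row of Table 2 ends lirilumab.

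**Lirilumab elsewhere.** Section 5.3.3, for immune-oncology events, allows a restart at Grade 1 or lower, or baseline, with listed exceptions. Section 5.3.4 lists the events after which lirilumab is stopped for good.

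**5-azacytidine step.** Section 5.3.2 states: "Dose reductions of azacytidine will be as per Table 1". It goes on: "Thus, if dose level 0 is established as the MTD, one and two dose level reductions of azacytidine will be azacytidine 50 mg/m²", with 25 mg/m² as the second step. For a lower MTD, "further dose reduction levels of 5-azacytidine will be defined before moving to the phase II portion of the study". Section 5.2.1.2 speaks of "dose reductions or escalations of 5-azacytidine beyond those mentioned in table 5", but Table 5 is the response stopping table in section 11.2.

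**The concern.** After the same severe event, a treating physician can find an instruction to resume lirilumab and an instruction never to give it again. Following Table 2 as written would re-expose a patient to the antibody after an event that the protocol itself treats as grounds for permanent discontinuation. The two texts stand together in the lead-in and in phase II.

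The 5-azacytidine wording is a smaller matter. Table 2 counts reductions in dose levels, and 5.3.2 refers these to Table 1. That table is the cohort ladder, and 5-azacytidine stays at 75 mg/m² across its top three rows.

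**Working it through.** **1. Lirilumab: the two rules side by side.** Inputs are Table 2 (5.3.2), the restart rules in 5.3.3 and the discontinuation list in 5.3.4. No arithmetic applies.

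| Drug-related event | Table 2 | 5.3.4 |
|---|---|---|
| Grade 4, other than the isolated amylase/lipase and electrolyte exceptions | Resume at prior dose on recovery | Permanent stop |
| Grade 3 uveitis, pneumonitis, bronchospasm, diarrhea, colitis, neurologic event, hypersensitivity or infusion reaction (eight types), any duration | Resume at prior dose on recovery | Permanent stop |
| Other Grade 3, non-skin and non-laboratory, lasting over 7 days | Resume at prior dose on recovery | Permanent stop |
| AST or ALT above 8 times ULN | Resume at prior dose on recovery | Permanent stop |
| Grade 3 outside the eight types, 7 days or less | Resume at prior dose on recovery | No stop required |
| Grade 3 skin event | Resume at prior dose on recovery | No stop required |
| Grade 3 laboratory abnormality without the AST/ALT criterion | Resume at prior dose on recovery | No stop required |

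The first four rows conflict and the last three do not. Table 2 can also stand for persistent Grade 2 events in general and for events attributed to 5-azacytidine alone.

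Two examples:
- Grade 3 drug-related pneumonitis resolved by day 10: Table 2 restarts, because recovery came within 14 days. 5.3.4 stops lirilumab permanently.
- A first Grade 4 non-laboratory event that recovers within 14 days: Table 2 restarts, 5.3.4 stops.

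**2. Lirilumab: the restart threshold.**
- Recovery within 14 days: Table 2 uses Grade 1 or lower, in line with the general threshold of 5.3.3.
- 15 to 28 days: Table 2's Grade 2 condition is a minimum. Waiting for Grade 1 satisfies both rules.
- Third to fifth occurrence: Table 2 says to follow to Grade 2 or lower and then resume, which reads as the point of restart. For an immune-oncology event, 5.3.3 waits for Grade 1 or baseline unless an exception applies. Take a third lirilumab-related Grade 3 skin event that has fallen to Grade 2. Table 2 resumes. 5.3.3 does not, because its Grade 2 skin allowance is closed to patients who have had a Grade 3 skin event.

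**3. 5-azacytidine: reproducing the plan's example.** Table 1 (5-azacytidine mg/m² / lirilumab mg/kg) gives level 0 = 75/3.0, -1 = 75/1.0, -2 = 75/0.3, -3 = 50/0.3 and -4 = 25/0.3.

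| From level | One and two rows down | One and two distinct 5-azacytidine doses down |
|---|---|---|
| 0 | 75, 75 | 50, 25 |
| -1 | 75, 50 | 50, 25 |
| -2 | 50, 25 | 50, 25 |

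The plan's figures of 50 and 25 for level 0 are reproduced only by stepping through distinct doses. That fixes the intended ladder as 75, 50, 25 mg/m².

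**4. Re-escalation in 5.3.6.** Here levels are counted by Table 1, and at least six patients must already have been treated at the next higher level. A patient cut to 50 mg/m² while staying on lirilumab 1.0 or 3.0 is on no row, because 50 is paired only with 0.3. By row, the next level above 50 is level -2. That cohort opens only if level -1 fails: "in 0 or 1/6 at dose level -1, then dose level 0 will be evaluated". When escalation succeeds, the condition read literally cannot be met.

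**The case against.** **On lirilumab.** The best defence is that the sections have different jobs. Table 2 modifies doses and 5.3.4 discontinues, so Table 2 naturally applies to patients who have not been discontinued. Section 5.3.3 already refers twice to the discontinuation criteria, and 5.3.2 opens by asking which drug is responsible. This is how a careful physician would probably proceed, and attribution does remove events due to 5-azacytidine alone. But Table 2 carries no such pointer and names Grade 4 in the row that ends in resuming lirilumab. For lirilumab-related Grade 4 events, 5.3.4 leaves little beyond the isolated amylase/lipase and electrolyte exceptions for that row to cover. Appendix G might add restart guidance. It is listed but not reproduced, so this cannot be checked.

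**On 5-azacytidine.** A reader might infer that a level -1 patient's mandated reduction is 75 to 75, no reduction at all. The documents do not support that. Moving from level -1 to -2 changes only lirilumab, which 5.3.2 forbids. Table 2 requires a dose below the current one, the worked example gives 50 and 25, and 5.3.7.2 treats 75 to 25 as more than one level. What stands is that a patient treated before the MTD is set must have the step inferred from an example conditional on level 0 being the MTD. Sections 5.3.7.1 to 5.3.7.4 soften this with discretionary reductions and a separate route to re-escalation.

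**Conclusion.** The lirilumab instructions are wrong as written and should be fixed for patient safety. The conflict covers nearly all drug-related Grade 4 events, the eight Grade 3 types, longer-lasting other Grade 3 non-skin, non-laboratory events, and the AST/ALT criterion. A narrower threshold mismatch with 5.3.3 arises at the third to fifth occurrence. This assumes that drug-related in 5.3.4 means related at least in part to lirilumab, and that nothing in Appendix G sets an order of precedence.

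Two stronger readings should be resisted:
- A reader might put a patient count on the conflict from the enrolment totals or the 30% toxicity limit. Those count patients exposed or patients with any drug-related Grade 3/4 event. They are not split by drug, type or duration, and no rate for the conflicting events is given.
- A reader might infer that every cycle 1 event at level -1 must come to restart before the MTD is known. Section 3.0 makes lead-in cycles at least 28 days, 5.2.2.1 sets only a floor ("cycle 2 should not be started before 28 days for the patients being treated on the lead-in cohort"), and holds may run beyond 28 days. The timing does not follow.

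The 5-azacytidine point is a minor clarification. Practical harm is limited by the single-center setting and the explicit wording of 5.3.4. DLT counts, the MTD rule, sample size and stopping boundaries do not change.

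**What to change.** Main edit: add to Table 2 that any lirilumab restart is subject to the discontinuation criteria in 5.3.4 and, for lirilumab-related immune-oncology events, to the recovery threshold in 5.3.3.

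Companion edits:
- In 5.3.2, state that one 5-azacytidine level means 75 to 50 to 25 mg/m², at any lirilumab dose, from the first lead-in patient.
- Use the same ladder for re-escalation in 5.3.6, and keep Table 1 as the cohort ladder only.
- Correct the reference to Table 5 in 5.2.1.2.

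The cost is a few sentences by amendment, with no added patients or procedures.
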